	 If applicable in accordance with routine clinical practice, the following schedule of assessments is recommended: Registry Inclusion Visit, at the time of enrolment into the Registry with the signature of the informed consent; Registry Baseline Visit, corresponding to the time in which the observational period will start; Six-month and Yearly follow-up visits for all patients included in the registry; Unscheduled follow-up visits, such as but not limited to, three months after Lamzede treatment start, or whenever deemed appropriate according to treating physician's judgement for patients that start the Lamzede treatment within one year priori to Registry participation.
	As patients can start Lamzede treatment at any time during the course of their participation to the Registry, if applicable in accordance with routine clinical practice, a baseline visit is recommended to be repeated before Lamzede administration starts and unscheduled visits are recommended as detailed in the setting of patients starting Lamzede treatment within one year prior to inclusion in the Registry. On the other hand, the patients can also terminate the Lamzede treatment at any time

Clinical Protocol Number: CLI-LMZYMAA1-12 Clinical Protocol Version Number: 8.0

	during the course of their participation to the Registry, and will be allowed completing in any case the 15-year follow-up period.
	This Registry will be conducted under conditions of routine clinical care, without mandatory diagnostic procedures and assessments that can be considered as outside of routine clinical care. Data collection will coincide with routine care visits only according to the judgement of the treating physician's. Data collection including retrospective data will be allowed.
	Since this is an observational study capturing only the outcomes of routine clinical practice, participation in the Registry will not change the patient/physician relation, nor influence the physician's drug prescription or therapeutic or other management of the patient. It is foreseen that approximately 40 suitable centres in the European Union (EU) will be involved and additional sites may be added, as required. The final list of countries and sites will depend on the Lamzede authorisation and capability of the site to administer the treatment. Indicatively, the following countries will be involved: Germany, Denmark, Sweden, Norway, The Netherlands, Austria, Spain, France, UK, Italy, Belgium and Poland.

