Population:	The eligible patient population for this Registry includes any patient in the EU with alpha-mannosidosis who is willing to participate, and who meets the inclusion criteria for this Registry. Patients will be offered the Registry participation over a 15-year follow-up period. Due to the observational nature of the present Registry study, patients can start or stop Lamzede treatment at any time during this 15-year observational period.
	 Eligibility criteria for the Registry are as follows: Inclusion Criteria Patients must meet all of the following inclusion criteria to be eligible for enrolment in the Registry: 1. Evidence of a personally signed and dated informed consent form indicating that the patient (or parents or a legally acceptable representative according to local regulation) has been informed of all pertinent aspects of the Registry and confirms the willingness to participate to the present observational study and to permit the investigator to enter assessment data recorded prior to Registry entry if available in the patient's medical records. 2. Diagnosis of alpha-mannosidosis (based on historical or current diagnosis).
	 Exclusion Criteria There are no exclusion criteria for the Registry. Moreover, patients participating in other clinical trials of any placebo, drug or biological substance conducted under the provisions of a

Clinical Protocol Number: CLI-LMZYMAA1-12

	protocol will not be prevented to participate to the Registry at the	
	discretion of the Investigator.	

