Data Sources: Study Size:	 Vital signs: systolic (SBP) and diastolic blood pressure(DBP), pulse rate (PR) Electrocardiogram (ECG) Laboratory tests (haematology and chemistry) Physical Examination Other Variables In addition the following other variables will be presented: Height, weight, Body Mass Index (BMI) and rate of growth Hearing test (Pure Tone Audiometry) Concomitant procedures and medications Data sources will include patient medical records and any other records of clinical findings or observations collected as part of routine clinical practice. Retrospective data collection for any relevant measurement present in the patient's clinical records prior to the inclusion in the study will be allowed. The source data will be collected by the investigator in the patient file and captured in the electronic Case Report Form (eCRF). All patients with alpha-mannosidosis who are willing to participate will be included in the Registry. The size of the registry study is not based on the power to demonstrate a formal statistical hypothesis. However, some scenarios are presented in the table below, considering different proportions of GTR in naïve patients able to perform the functional tests after 3 years of treatment. The proportion of responders, the corresponding expected 95% confidence interval and the confidence width are shown below, assuming that at least 70 treated patients will be enrolled. In this case, it is expected that an exact (Clopper-Pearson) two-sided 95% confidence interval (CI) might be provided with a width ranging from 0.239 (worst case) to 0.199 (best case) assuming GTR of 0.60 or more. Of note, in all scenarios the lower limit of 95% CI is always greater than 45% which is considered a clinical relevant result. 					
	Broate	Expected Proportion	95% CI Lower Limit	95% CI Upper Limit	95% CI Actual width	
		0.60	0.476	0.715	0.239	
		0.65	0.527	0.760	0.234	
		0.70	0.579	0.804	0.225	
		0.75	0.632	0.846	0.214	
		0.80	0.687	0.886	0.199	
Data Analysis:	Categorical variables will be described by means of absolute and relative frequencies, while continuous variables by means of mean, standard deviation, quartiles, min and max.					

Clinical Protocol Number: CLI-LMZYMAA1-12

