9.2.6 Study Plan

The Registry will be conducted under conditions of routine clinical practice, without Registry-mandated diagnostic procedures and assessments that can be considered as outside of routine clinical care by the treating physician. Data collection will coincide with routine care visits only according to the judgement of the treating physician. Patients' data collection including retrospective data will be performed.

If applicable in accordance with routine clinical practice, the following schedule of assessments is recommended, as presented in Table 1 and previously described in section 9.1 concerning study design.

Since this is an observational study capturing only the outcomes of routine clinical practice, participation in the Registry will not change the patient/physician relation, nor influence the physician's drug prescription or therapeutic or other management of the patient.

Lamzede has to be administered in accordance with the current Lamzede SmPC and in line with usual clinical practice.

If further medicinal products will be applied besides Lamzede® for the treatment of alpha mannosidosis all medicinal products have to be administered in accordance with their respective SmPCs and in line with usual clinical practice.

Clinical Protocol Number: CLI-LMZYMAA1-12

Clinical Protocol Version Number: 8.0

Date: 01 February 2019

Table 1 Schedule of Assessments to be reported (Flow-Chart).

Procedure	Registry Inclusion visit	Registry Baseline visit	Unscheduled Follow-up Routine	Six-month Follow-up Routine	Yearly Follow-up Routine
	(approx 7 days)	(Time 0)	Clinical Visits ¹	Clinical Visits ²	Clinical Visits
Administrative					
Informed consent form	Х	X ³			
Inclusion/exclusion	Х	X ³			
criteria					
Medical and disease	X	X ³⁻⁴			
history (including					
disease onset, residual					
enzymatic activity,					
genotype mutations,					
bone marrow					
transplantation) and					
concomitant illnesses					
Previous and		X4	X	X	X
concomitant					
medications, including					
Lamzede in hospital or					
home infusion setting					
Concomitant procedures	Х	Х	X	X	X
Physical examination ⁵		Х	X	X	X
(Vital signs and					
anthropometric					
measurements, including					
rate of growth)					
Demographics	X	X ³			
Administration of medica	ation			•	
Lamzede therapy, in		Х	X	X	X
hospital or home					
infusion setting ⁶					
Assessments ⁷					
Anti-velmanase alfa-IgG		Х	X		X
antibody (ADA) ^{7a}					
Standard haematological		Х	X		X
tests ^{8a}					

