Laboratory chemistry ^{8b}		Х	X		X
Oligosaccharides in		Х	X		X
serum ^{7a}					

Clinical Protocol Number: CLI-LMZYMAA1-12

Clinical Protocol Version Number: 8.0

Date: 01 February 2019

Procedure	Registry Inclusion visit (approx 7 days)	Registry Baseline visit (Time 0)	Unscheduled Follow-up Routine Clinical Visits ¹	Six-month Follow-up Routine Clinical Visits ²	Yearly Follow-up Routine Clinical Visits
Serum Immunoglobulin class G, A, M ^{7a}		Х	X		X
Three-minute stair climbing test (3MSCT) ⁹ , when applicable		Х			X
Six-minute walk test (6MWT) ⁹ , when applicable		Х			X
Two-minutes walk test (2MWT) ¹⁰ , when applicable		X			X
Forced vital capacity (L and % of predicted)		Х	X		X
Electrocardiogram		Х	X		X
Hearing test (PTA)		Х	X		
Infections (including length and antibiotics requirement)		Х	X		X
Psychotic events		Х	X		X
Adverse Events /Adverse Drug Reactions ¹¹	X	Х	Х	Х	X
Health Assessment Questionnaires					
EQ-5D-5L		Х			X
Zarit Burden Interview		Х			X
CHAQ		Х			X
Behavior Checklists ¹²		Х			X

Abbreviations: ADA, anti-velmanase alfa-immunoglobulin G (IgG) antibody; CHAQ, Childhood Health Assessment Questionnaire; EQ-5D-5L, European Quality of Life Five Dimension Five Level Scale; L, litre; PTA, pure tone audiometry

1. Unscheduled follow-up visits can be performed at, but not limited to, three months after Lamzede treatment start, or whenever deemed appropriate according to treating physician's judgement for patients that start Lamzede treatment within one year prior to Registry inclusion.

2. Additional follow-up visit after six months is highly recommended for patients that start Lamzede treatment within one year prior to Registry inclusion.

- 3. If not taken or collected at Registry Inclusion visit.
- 4. Patients' retrospective data may be collected at the time of Registry enrolment if available. Baseline visits are recommended to be repeated for those patients who will start Lamzede therapy during the course of the study, before therapy is initiated.
- 5. Physical examination to collect vital signs, anthropometric measurements like height, weight, rate of growth and the ability to perform the endurance test at the study visit.
- 6. If applicable, information regarding weekly Lamzede therapy received by the patient need to be recorded within all the Registry duration

Clinical Protocol Number: CLI-LMZYMAA1-12	
Clinical Protocol Version Number: 8.0	Date: 01 February 2019

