- 7. All assessments mentioned in the above table will be collected only if considered necessary and available as part of routine clinical practice by the treating physician and no additional tests specific to the Registry will be done.
 - 7a. The markers (oligosaccharides in serum, IgG, IgA and ADA) will not be evaluated by a central laboratory for German patients only, while markers testing will take place according to local routine clinical practice in Germany.
- The markers oligosaccharides in serum, IgG, IgA and ADA) will be evaluated through a central laboratory in EU countries other than Germany.
- 8. Standardtest for haematology and chemistry assessed by local laboratory if available per clinical practice of the site:
 - a. Haemoglobin, haematocrit, platelet count, red blood cells, white blood cells with differential count (band forms, segment forms, neutrophils, eosinophils, basophils, monocytes, lymphocytes) (all expressed in % as well as in absolute numbers). Blood smear for leukocytes detection by electronic microscopy may be done at the treating physician's discretion.
 - b. Biochemistry: Serum electrolytes (sodium, potassium, calcium, inorganic phosphate), creatinine, creatinekinase, amylase, AST, ALT, ALP, albumin, bilirubin (total and direct), LDH.
- 9. In patients from 4 years of age and when applicable according to the judgment of treating physician.
- 10. In patients *below* 4 years of age and when applicable according to the judgment of treating physician.
- 11. Adverse Events /Adverse Drug Reactions based on all risk categories associated with Lamzede EU RMP, including infusion related reactions (IRRs) and hypersensitivity (as identified risks), acute renal failure, loss of consciousness and medication errors (as potential risks). Data on pregnancy and lactation (as missing information) will be also collected if available.
- 12. One of the Behavior Checklists (CBCL prescholar-scholar, ABCL/ASR (self-reporting), OABCL) will be used to the applicable age and according to the judgment of treating physician.

9.3 Variables

Only available evaluations as decided by the treating physician based on local routine clinical practice will be collected in the Registry. Patients' retrospective data may be collected if available. Where there are no data to report, this will be indicated in the applicable section(s) of the eCRF. See Table 1 for the schedule of assessments to be reported.

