9.7 Data Analysis

The following describes the statistical analysis as it is foreseen at the time of planning the trial. Detailed methodology for the summary and statistical analyses of data collected in this study will be documented in a Statistical Analysis Plan (SAP).

9.7.1 Populations for Analysis

The following analysis sets will be defined:

- The Lamzede Safety analysis set (L-SAF) will contain all enrolled patients fulfilling inclusion criteria who have, at some time, received Lamzede treatment. This will include all patients entering the study currently taking Lamzede and all patients not taking Lamzede on entry to the study, but who begin doing so during the study. The latter group (those not taking Lamzede on entry to the study, but who begin doing so during the study) will only be classed as in the L-SAF from the time that they begin taking Lamzede. As is common practice, patients who have taken any amount of Lamzede, even if only one dose, will be included in the safety analyses. With regards to L-SAF definition, a minimum individual follow up of 1 month after last dose taken will be proposed. A consequence of this approach, where patients can be in the L-SAF for very varying amounts of time is that adverse event (and adverse reaction) rates will be presented based on person-years at risk, and not simply based on the total number of patients who are ever in the L-SAF.
- The Lamzede Effectiveness analysis set (L-FAS) will contain patients included in the Lamzede Safety analysis set at the times when they have been taking Lamzede, and for 12 months thereafter excluding patients without any valid measurement and those with major protocol deviations affecting the effectiveness evaluations. The consequence of this is that

Clinical Protocol Number: CLI-LMZYMAA1-12	
Clinical Protocol Version Number: 8.0	Date: 01 February 2019

"baseline" will be clearly defined for each patient – namely the time they started to take Lamzede, not necessarily the time they enter the study. So a patient can be excluded from the L-FAS for some of their time in the study, and then join the L-FAS. In such cases, their "baseline" would be the time when they started.

- The No-Lamzede Safety analysis set (NL-SAF) will include patients only for the time when they are not (and have not within 1 month) been taking Lamzede.

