9.9 Limitations of the Research Methods

The Registry is a multi-centre, multi-country, non-interventional, prospective cohort in alpha-mannosidosis patients. The Registry will be conducted under conditions of routine clinical care and will include all eligible patients with alpha-mannosidosis who agree to participate. The decision to start treatment with Lamzede can be taken at any time during the course of the Registry. Based on the current unmet medical need patients can start the treatment independently from the Registry set up.

The study will involve collection of primary data directly from healthcare professionals. The data collected are expected to provide evidence of the long-term safety and effectiveness of Lamzede in the treatment of alpha-mannosidosis in patients under conditions of routine clinical care; moreover, the data collected on the natural history of the disease are expected to expand the knowledge on the pathology itself. Only available evaluations as decided by the investigator and based on local clinical practice will be collected. Where there are no data to report there will be no information recorded in the applicable section(s) of the eCRF. Therefore, the assessments performed and data provided from different study sites may vary depending on local clinical practice. Assessments will generally be interpreted locally by the investigators, rather than centrally, therefore there may be differences between sites for the outcomes of evaluations.

In case a patient is transferred to another continuing care site during the 15-year observational period, the new treating site will be formally involved in the Registry study following a request of authorization submitted to the relevant Ethics Committee and Regulatory Authority to complete the 15-year observational period following the patient and collecting all information as per study protocol Data will be collected prospectively after enrolment in the Registry. However, retrospective data may be collected. The availability and quality of these retrospective data may be variable.

It is acknowledged that patient self-selection into a study of this nature is inevitable as due to the willingness of the patients to participate and, without a randomised control arm, such selection could introduce bias. Such bias, however, will always be of unknown size and direction. All reports and publications from the study will clearly describe these potential limitations.

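### Entry of pre-Lamzede values is optional almost everywhere but stated as a fixed plan in 9.2.6, although the effectiveness baseline of patients already on Lamzede at enrolment can come only from such values

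*Protocol*

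**What the plan says.** The protocol sets the status of retrospective data in several places, with different force:

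- Abstract, Study Design: "Data collection including retrospective data will be allowed".
- Abstract, Data Sources, and again in 9.4: "Retrospective data collection for any relevant measurement present in the patient's clinical records prior to the inclusion in the study will be allowed".
- Table 1 footnote 4: "retrospective data may be collected at the time of Registry enrolment if available".
- Section 9.3: "retrospective data may be collected if available".
- Section 9.9: "However, retrospective data may be collected. The availability and quality of these retrospective data may be variable".
- Section 9.2.6, alone in this: "data collection including retrospective data will be performed".

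Inclusion criterion 1 has the patient "permit the investigator to enter assessment data recorded prior to Registry entry if available" in the medical records. This secures permission but puts no duty on the site.

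Section 9.7.1 builds the L-FAS from the Lamzede safety set, which includes patients who are on Lamzede when they enter. It fixes each patient's baseline as "namely the time they started to take Lamzede, not necessarily the time they enter the study". Section 9.7.4 presents the effectiveness variables as actual values and, where applicable, as change from baseline by time point. Section 9.7.7 says that missing values are not replaced. Section 9.2.1 foresees about 30 patients from earlier Lamzede trials.

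**The concern.** A permissive rule does little harm for background history. Here it governs the reference value of an effectiveness summary. For a patient already on Lamzede, the Registry Baseline Visit (Time 0 in 9.1) takes place on treatment. The pre-treatment value lies in older records, and whoever decides whether to enter it already knows how the patient has done.

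Two things are at stake. If the decision is related to the patient's course, the change-from-baseline summaries and individual profiles of the longest-treated patients are distorted. If values are simply not entered, these patients have no change score, and a registry meant to give long-term data loses part of its longest exposure. Neither can be repaired at analysis, because no analysis plan can recover a value that a site was free to leave out.

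**Working it through.** **Step 1: which rule applies?** A site that follows the abstract, footnote 4, 9.3, 9.4 or 9.9 may enter nothing and still comply. A site that follows 9.2.6 is expected to enter retrospective data. The protocol does not say which wording prevails.

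**Step 2: who needs these data?** For a patient enrolled while on Lamzede, first dose precedes enrolment. The L-FAS baseline is at first dose. Hence the baseline precedes enrolment, and every baseline value is retrospective. With no entered value and no replacement, there is no change score.

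**Step 3: can a missing entry be told from a missing record?** Section 9.3 says the eCRF will indicate that there are no data to report. Section 9.9 says nothing is recorded in that case. Under 9.9, a blank may mean that no value exists or that an existing value was not entered. Monitoring under 9.8.2 covers completeness and comparison with source, but a blank in an optional field breaches no rule.

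**Step 4: does it reach the GTR?** Section 9.7.4 restricts the GTR rate to naïve patients after 3 years of treatment and does not define naïve.

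- If it means naïve at registry entry, patients already on Lamzede are outside the GTR and the rate is untouched.
- If it means naïve at Lamzede start, they are inside. The oligosaccharide criterion (below 4 µmol/L) is an absolute level and needs no baseline. The other five criteria (3MSCT, 6MWT, FVC, CHAQ DI, CHAQ pain) are changes. A patient with no baseline can then be assessed in one domain only, while response requires two.

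**Step 5: the plan's own figures.** The exact intervals in 9.5 reproduce. With n = 70 and x = 70p, the lower limit is the 0.025 quantile of Beta(x, n − x + 1) and the upper limit is the 0.975 quantile of Beta(x + 1, n − x). For p = 0.60 (x = 42) this gives 0.476 to 0.715, width 0.239. For p = 0.80 (x = 56) it gives 0.687 to 0.886, width 0.199. All five rows match. They concern the GTR in naïve patients; the protocol gives no n for the change-from-baseline summaries.

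**Step 6: direction of bias, by assumption only.** Let p be the true share improved, and let a and b be the chances that a baseline is entered for improvers and non-improvers. The share improved among patients with an entered baseline is pa / (pa + (1 − p)b). The entry rates below are assumed, not taken from the protocol. With p = 0.60:

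| a | b | Calculation | Apparent share |
|---|---|---|---|
| 0.8 | 0.8 | 0.48 / 0.80 | 0.600 |
| 0.9 | 0.7 | 0.54 / 0.82 | 0.659 |
| 0.9 | 0.5 | 0.54 / 0.74 | 0.730 |
| 0.7 | 0.9 | 0.42 / 0.78 | 0.538 |
| 0.5 | 0.9 | 0.30 / 0.66 | 0.455 |

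Equal entry rates give no bias. Unequal rates move the result either way.

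**The case against.** The case on the other side is substantial.

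- **The wordings can be read together.** The permissive phrases may only allow sites to look back before enrolment and admit that records are uneven, with 9.2.6 stating the working plan. That is a possible reading, but the text does not give it, and 9.9 still leaves a blank uninterpretable.
- **Safeguards exist.** Section 9.3 asks for absent data to be indicated, 9.8.2 provides for completeness checks, and 9.9 discloses variable availability and quality. They help, but disclosure does not remove the choice over values that do exist, and 9.3 and 9.9 disagree.
- **The former trial patients may be well documented.** Section 7.1 describes a pooled trial database (rhLAMAN-10) from which changes over time were reported, so their pre-treatment values were recorded. This makes wholesale loss of their baselines unlikely. The protocol does not, however, describe how those values reach the registry.
- **A baseline rule may sit in the analysis plan.** Which value counts as baseline can be settled there. The duty to enter it belongs in the protocol and eCRF instructions.

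A reader might also infer three stronger things, which the documents do not support. First, that entry will in fact be selective and overstate effectiveness: the text shows discretion, not selection, and the bias could run either way. Second, that the primary response rate is compromised: the restriction to naïve patients may exclude this group altogether. Third, that 30 of 70 treated patients (43%) are affected: the 70 in 9.5 is an assumption for GTR precision, and 9.2.1 does not say that the 30 are among them.

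**Conclusion.** The point holds in limited form. The protocol states two different obligations for retrospective data, and its own baseline definition makes those data indispensable for everyone already on Lamzede at enrolment. Their L-FAS change from baseline depends on entry that most sections leave to the site after the course is known. The summaries could be biased in either direction, or these patients could drop out of them.

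The size cannot be derived from the protocol. The documented facts are the roughly 30 patients foreseen from earlier trials and the possibility of others who started after authorisation on 23 March 2018 and before enrolling (data collection planned from 30 September 2019). The figures in step 6 illustrate direction and rest wholly on assumed entry rates.

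Whether the GTR is touched depends on the meaning of naïve. For an outer bound, assume the wider meaning, that the 30 are among the 70, and that none has a usable baseline. Then n = 40, and at 0.60 the exact interval is 0.433 to 0.751 (width 0.318), with a lower limit under the 45% mentioned in 9.5. None of these three assumptions is established by the protocol.

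The wording should be settled before sites start entering data. It does not put the design as a whole in doubt.

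**What to change.** Use one rule in the abstract, 9.2.6, Table 1 footnote 4, 9.3, 9.4 and 9.9:

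- For every patient treated with Lamzede before enrolment, the last existing value of each effectiveness variable before the first dose is entered, with its date, whenever it is in the medical records.
- Where there is none, the eCRF records *not in records*. This also reconciles 9.3 with 9.9.
- Monitors check this item under 9.8.2.
- Reports state how many patients treated before enrolment have a true pre-treatment baseline.
- Other retrospective data stay optional.

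The cost is a change of wording in the protocol and eCRF instructions and some one-time data entry at sites. No test or visit is added, so the registry stays non-interventional, and the consent required by inclusion criterion 1 already covers entry of these records.
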